We have developed a CDSS tool that aims to empower improvement in overall AF-related care, not simply with regards to antithrombotic management, but also to support effective rate control and treatment of AF risk factors. The tool has been assessed in a preliminary fashion by a general cardiologist, electrophysiologist and primary care physician, working independently to assess the

utility and dependability of the CDSS using mock clinical cases. While it functioned accurately and with seeming efficacy, there remains the need to determine applicability, ease of use and clinical effectiveness in terms of whether AF patient care and outcomes would improve at the population level with its use.

The primary aim of Integrated Management Program Advancing Community Treatment of Atrial Fibrillation (IMPACT-AF) study is to evaluate whether a CDSS tool, available to primary care physicians, and designed to support both practitioners and patients with evidence-based AF management, can improve clinical and patient-reported outcomes by comparison to usual clinical care. It further seeks to establish whether it will better standardize process of care so as to produce more efficient and cost-effective use of time and scarce health care resources as compared to usual care.

Methods

IMPACT-AF is a prospective, randomized, un-blinded, cluster design clinical trial, conducted in the primary care setting of Nova Scotia, Canada.

At least 200 primary care providers are being recruited and randomized at the level of the practice to control (usual care) or intervention (eligible to access to CDSS) cohorts. Over 1,000 patients of participating providers with confirmed AF will be managed per their provider's respective assignment.

Outcomes

Primary Outcome

The IMPACT-AF primary outcome is composite of any AF-related emergency department visit or unplanned CV hospitalization over 12 months.

Secondary Outcomes

Secondary outcomes include comparing the intervention versus usual care over 12 months on the following:

- 1. Any AF-related emergency department visit
- 2. Unplanned cardiovascular (CV) hospitalization
- 3. Strokes
- 4. Systemic embolism / major bleeding
- 5. Mortality
- 6. Anticoagulant therapy
- 7. Access to specialist consultation

- 8. Echo
- 9. Catheter ablations
- 10. EQ5D
- 11. Health care costs

The definitions of all outcome variables for the primary and secondary analyses are found in Appendix 1.

Analysis Plan

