This statistical analysis plan follows the JAMA Guidelines for the Content of Statistical Analysis Plans in Clinical Trials ¹³. A summary of all planned analyses is provided in **Table 1**.

Blinded Analyses

All statistical analyses will first be completed using blinded treatment groups (i.e. treatment X and Y).

Presentation of Data

The trial results will be presented according to the CONSORT guidelines for randomized controlled trials (RCTs) 14 . The baseline demographic characteristics of the patients will be summarized by group, reported as a mean (standard deviation [SD]) or median (first quartile, third quartile) for continuous variables and count (percent) for categorical variables (**Tables 2**). All statistical tests will be 2-tailed with α =0.05.

Primary Outcome Analysis

The primary efficacy analysis will be an analysis to compare rates of the composite of any AF-related emergency department visit or unplanned CV hospitalization between Intervention and Usual care over 12 months, with the outcome being treated as number of events (Tables 3). The analysis will follow the intention-to-treat (ITT) principle. While the unit of randomization is the practice/physician, the unit of analysis will be the patient. We will use Generalized Estimating Equations (GEE) —assuming exchangeable correlation structure for patients within the same practice and adjusting for urban and rural practice types to analyze all outcomes¹⁵. Unlike ordinary regression techniques, GEE allows us to estimate the intra-practice correlation among patients within each practice. For time-to-event analysis this is done using frailty-models. The results will be reported as estimate of the effect—reported as hazard ratio [HR], corresponding 95% confidence interval and associated p-values. All p-values will be reported to three decimal places with those less than 0.001 reported as p<0.001. The criterion for statistical significance will be set a priori at alpha = 0.05. The answers to the five questions in the EQ-5D-5L will be converted to health utilities using the Canadian scoring algorithm¹⁶. Cost effectiveness analysis

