will be conducted by calculating the incremental cost per QALY gained by the CDSS arm compared with the usual care arm. Due to skewness of costs and health utility distributions, the non-parametric bootstrapping method will be used to estimate the 95% confidence interval for the incremental cost per QALY gained. All analyses will be performed using SAS version 9.4 (Cary, NC).

Secondary Outcomes Analysis

We will estimate the effect of CDSS (intervention) versus usual care (control) over 12 months on the following: any AF-related emergency department visit; unplanned CV hospitalization; strokes; systemic embolism / major bleeding; mortality; anticoagulant therapy; access to specialist consultation; echo; catheter ablations; EQ5D; health care costs (Table 3). The subgroup analyses will be performed by adding an interaction term of the subgroup variable and the intervention variable in the model. The criterion for statistical significance for subgroup analyses will be set at alpha = 0.05. This will not be adjusted for multiple testing as these analyses are exploratory.

Sensitivity Analyses

There are several methods for analyzing cluster RCTs^{17, 18}. We will conduct sensitivity analyses in two ways. Firstly, we will perform sensitivity analyses using commonly used patient-level methods such as random-intercept model method (Table 4a). Secondly, we will also perform sensitivity analyses with the outcome (composite of any AF-related emergency department visit or unplanned CV hospitalization) being treated as a count assuming a Poisson distribution (Table 2). The results will be reported as incidence rate ratio [IRR], 95% CI and associated p-value. We hypothesize that our results will remain robust to the different sensitivity analyses.

Subgroup Analyses

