A subgroup analysis will be conducted to compare the effect of CDSS (intervention) versus usual care (control) on the composite of any AF-related emergency department visit or unplanned CV hospitalization, as well as the of number AF Related ED Visits and CV Hospitalizations individually, by location of practice, patient sex, age, CHADS2, CHADS-VASC, hypertension, diabetes and years of practice of family doctor. We will perform these subgroup analyses by regression methods with appropriate interaction terms. This subgroup analysis will be conducted for all primary and secondary outcomes (Tables 5a, 5b and 5c). Our hypothesis is that the effects of the intervention on outcomes differ by subgroups. A sensitivity analysis will equally be conducted for all the different subgroup analyses with the outcome being treated as a count (Tables 5a, 5b and 5c). All the subgroup results will be presented using forest plots reporting estimates of effect as HR or IRR, 95% CI for each subgroup and a p-value of the interaction test.

Dissemination

Upon trial completion, the primary manuscript with the 12-month follow-up results, whether positive, negative or neutral, will be submitted for a peer-reviewed publication to a top medical journal. The final dataset will be shared through an open access data repository once all analyses are completed.

References

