1) Primary To compare rates of the composite of any AF-related emergency department visit or unplanned CV hospitalization between Intervention and Usual care over 12 months	composite of any AF-related emergency department visit or unplanned CV hospitalization over 12 months	Intervention better than Usual Care	Generalized Estimating Equations (GEE) or frailty models
2) Secondary To compare I vs UC over 12 months on the following: any AF-related emergency department visit	any AF-related emergency department visit	Intervention better than Usual Care	GEE or frailty models
unplanned CV hospitalization	unplanned CV hospitalization	Intervention better than Usual Care	GEE or frailty models
strokes	strokes	Intervention better than Usual Care	GEE or frailty models
systemic embolism / major bleeding	systemic embolism / major bleeding	Intervention better than Usual Care	GEE or frailty models
mortality	mortality	Intervention better than Usual Care	GEE or frailty models
anticoagulant therapy	anticoagulant therapy	Intervention better than Usual Care	GEE or frailty models
access to specialist consultation	access to specialist consultation	Intervention better than Usual Care	GEE or frailty models
echo	echo	Intervention better than Usual Care	GEE or frailty models

catheter ablations	catheter ablations	Intervention better than	GEE or	frailty models
		Usual Care		
EQ5D	EQ5D	Intervention better than	GEE or	frailty models
		Usual Care		
health care costs	health care costs	Intervention better than	GEE or	frailty models
		Usual Care		
3) Subgroup Analyses:				
To compare the effect of I				
vs UC by different	All primary and	Effects on outcomes	Regres	sion methods with
subgroups: location of	secondary outcomes	differ by location of	approp	riate interaction
practice, patient sex,		practice	term	
age, CHADS2, CHADS-				
VASC, hypertension,				
diabetes and years of				
practice of family doctor				
4) Sensitivity Analyses:	composite of any	Results will remain	i)	patient-level
i) To assess the robustness	AF-related	robust		methods such as
of the results to different	emergency			random-intercept
methods of adjusting for	department visit or			model and
clustering;	unplanned CV			cluster-level [i.e.
ii) To assess the robust	hospitalization			random- and
ness of the results if the				fixed-effects
outcome is treated as the				meta-analytic]
count (number of events)			ii)	GEE using
				Poisson
				distribution

IMPORTANT REMARKS:

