- The GEE is a technique that allows to specify the correlation structure between patients within a hospital and this approach produces unbiased estimates under the assumption that missing observations will be missing at random. An amended approach of weighted GEE will be employed if missing observations are found not to be at random.
- In all analyses results will be expressed as coefficient, standard errors, corresponding 95% and associated p-values.
- Goodness-of-fit will be assessed by examining the residuals for model assumptions and chi-squared test of goodness-of-fit.

Table 2. Characteristics of the Study Populations at Baseline

Characteristic	haracteristic Variable		Usual Care (N=543)	
Age – years Median Interquartile range	Age at start			
Male sex - n (%)	Sex (Male)			
Height – cm - Mean (SD)	Height			
Weight – Kg- Mean (SD)	Weight			
Urban location of care - n (%)	Location			
Heart rate – BPM - Mean (SD)	Heart Rate			
Systolic Blood pressure - mmHg Median Interquartile range	Systolic BP			
Systolic Blood pressure - mmHg Median Interquartile range	Diastolic BP			
Type of atrial fibrillation - n (%)				
Paroxysmal	AF Classification (Paroxysmal)			
Persistent	AF Classification (Persistent/Chronic)			
Newly diagnosed/new onset	AF Classification (First Episode)			
PREVIOUS MEDICATION USE - n (%)				
Aspirin	Ingredient (Aspirin)			
other antiplatelet	Ingredient (TICLOPIDINE) or (PRASUGREL) or (TICAGRELOR) or (CLOPIDOGREL)			
Vitamin K antagonist (Warfarin)	Ingredient (Warfarin)			
Non-vitamin K antagonist (NOAC)	Ingredient (DABIGATRAN) or (RIVAROXABAN) or (APIXABAN)			
Beta-blocker	Ingredient (TIMOLOL) or (LABETALOL) or (CARVEDILOL) or (PINDOLOL) or (ACEBUTOLOL) or (PROPANOLOL) or (NADOLOL) or (ATENOLOL) or (BISOPROLOL)			
Calcium channel blocker	Ingredient (NIFEDIPINE) or (FELODIPINE) or (AMLODIPINE) or (AMLODIPINE + ATROVASTATIN) or (DILTIAZEM) or (VERAPAMIL)			
Digoxin	Ingredient (DIGOXIN)			
Any other antiarrhythmic	Ingredient (DRONEDARONE) or (QUINIDINE) or (PROCAINAMIDE) or (MEXILETINE) or			

	(SOTALOL) or (LIDOCAINE) or (FLECAINIDE) or (PROPAFENONE) or (AMIODARONE)		
Nonsteroidal anti- inflammatory	Ingredient (SULINDAC) or (PETOPROPHEN) or (PIROXICAM) or (KETOROLAC) or (TENOXICAM) or (TIAPROFENIC) or		
	(INDOMETHACIN) and (ETODOLAC) or (NEPAFENAC) or (IBUPROFEN) or		
	(MELOXICAM) or (NAPROXEN) or (DICLOFENAC) or (CELECOXIB)		
OAC contraindication	OAC Contraindication (Yes)		
OAC other reason not prescribed	OAC reason not Rxd (Yes)		

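### The SAP treats the primary composite as a number of events yet reports a hazard ratio, without assigning a time-to-event analysis to it or saying whether first or recurrent events are meant

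*SAP*

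**What the plan says.** Protocol 3.8 takes as its primary measure of effect the between-arm difference in the proportion of patients with at least one component event over 12 months, and derives 1,075 patients from it. Protocol 3.9 plans GEE for all outcomes and names no link, hazard ratio or time-to-event analysis.

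The SAP's Primary Outcome Analysis compares the composite "with the outcome being treated as number of events (Tables 3" and applies GEE to all outcomes. It then adds "For time-to-event analysis this is done using frailty-models", and has results "reported as hazard ratio [HR], corresponding 95% confidence interval and associated p-values". Table 1 gives the method in the primary row as "Generalized Estimating Equations (GEE) or frailty models". The same label stands on every secondary row, including EQ5D and costs.

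The count then returns as a sensitivity analysis. The Sensitivity Analyses section has the composite "being treated as a count assuming a Poisson distribution (Table 2", reported as an incidence rate ratio (IRR). Table 1 repeats this as the second sensitivity analysis, by Poisson GEE. For subgroups, "A sensitivity analysis will equally be conducted for all the different subgroup analyses with the outcome being treated as a count". Table 3 puts the hazard ratio (HR) under primary analysis and the IRR under sensitivity analysis.

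The table cited for the count analysis is the baseline table: "Table 2. Characteristics of the Study Populations at Baseline". The Outcomes section says "The definitions of all outcome variables for the primary and secondary analyses are found in Appendix 1". That appendix is not in the SAP text available for this review.

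**The concern.** This sentence governs the one confirmatory test of an unblinded trial. A GEE for a count estimates a rate ratio, so the stated outcome form cannot produce the stated effect measure. The count is also the SAP's own check on the primary result, so a literal reading leaves nothing to check it against.

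The choice has consequences. A few patients with many visits can drive a count, whereas each contributes only one event to a first-event analysis. The two can therefore reach different conclusions on the same data. If the form is not fixed before unblinding, more than one analysis could be defended as the planned one, and coding the arms X and Y does not prevent a choice by p-value.

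Separately, a reader of the protocol expects a difference in proportions. The SAP does not mention that measure or explain why it was replaced. Table 3 allows a crude difference to be worked out, but no shell gives one adjusted for clustering with a confidence interval.

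**Working it through.** **1. Which readings fit the text**

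| Reading | Fits | Conflicts with |
|---|---|---|
| Count, GEE, rate ratio | Outcome phrase; GEE for all outcomes | HR as effect measure; count as sensitivity analysis; Table 3 columns |
| Time to first event, practice frailty, HR | HR; frailty sentence; Table 1 option; Table 3 and 5a columns; count as a separate check | Outcome phrase only |
| Recurrent events, HR | HR; outcome phrase; titles of Tables 5b and 5c | Nothing explicit, but the count check becomes close to a repeat |

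The second reading fits best. The third is weaker but not excluded.

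**2. The plan's own figure**

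Inputs from Protocol 3.8: 50% versus 40%, two-sided alpha 0.05, power 80%, ICC 0.05, 9 patients per practice.

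- Unadjusted total: 2 × (1.96 + 0.84)² × (0.5×0.5 + 0.4×0.6) / 0.10² = 768.32
- Variance inflation: 1 + (9 − 1) × 0.05 = 1.4
- Adjusted total: 768.32 × 1.4 = 1075.65, as in Protocol Table 3

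The trial is therefore sized on a binary outcome.

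**3. Time to first event on the same inputs**

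Assume proportional hazards and complete 12-month follow-up.

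- HR = ln(1 − 0.4) / ln(1 − 0.5) = 0.737
- Effective events = 1075 × 0.45 / 1.4 = 345.5
- Power (Schoenfeld) = Φ(√(345.5/4) × |ln 0.737| − 1.96) = 81%

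**4. Literal count on the same sample**

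The documents give neither events per patient nor overdispersion. Assume rates −ln 0.5 = 0.693 and −ln 0.6 = 0.511 per patient-year, and the same inflation of 1.4, so 537 / 1.4 = 383.6 effective patients per arm. With φ the variance-to-mean ratio, SE² = φ × [1/(383.6 × 0.693) + 1/(383.6 × 0.511)].

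| φ | Power |
|---|---|
| 1 | 90% |
| 1.5 | 75% |
| 2 | 63% |
| 3 | 46% |

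This is for scale only. With these rates held fixed, overdispersion from patient heterogeneity would lower the share of patients with any event below 50% and 40%.

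**5. Simulation holding 50% versus 40% fixed**

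The design was 120 practices of 9 with binary ICC 0.05. Assumed: gamma patient heterogeneity with shape 0.5 to 5, giving control means of 1.87 down to 0.78 events; no urban/rural covariate.

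| Assumed effect | Rate ratio | Count power | First-event frailty power | Different significance conclusion |
|---|---|---|---|---|
| Scales every patient's rate | 0.575 to 0.714 | 88% to 90% | 81% to 84% | 11% to 13% of trials |
| Spares 20% of event patients all their events | 0.80 | 27% to 55% | 78% to 81% | 27% to 55% of trials |

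The test of proportions had 79% to 81% power in both settings and differed from the first-event test in only 4% to 5% of trials.

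**6. Recurrent-event HR against the Poisson rate ratio**

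With full follow-up and equal practice sizes the simulated log ratios were identical. With unequal practice sizes (assumed mean 9, coefficient of variation about 0.8), practice frailty and exchangeable GEE gave log ratios differing by 0.005 to 0.05 on average and by up to 0.27.

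**The case against.** The best defence is that one stray phrase is at fault and the rest of the SAP points one way. The paragraph itself supplies frailty models for time-to-event analysis just before it names the HR, Table 1 allows them, and Tables 3 and 5a to 5c list the HR with the IRR beside it. The titles of Tables 5b and 5c may speak of numbers of events only because those tables also hold an IRR column. Appendix 1 may define the event. Most of this stands, and an HR is very probably meant. It still does not settle which HR, and a label shared by every primary and secondary row cannot choose the primary model. Appendix 1 could settle first versus recurrent, but would not remove the conflict within the paragraph.

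Four stronger readings are tempting and are not supported:

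- **That the SAP never mentions time-to-event analysis.** It does. What is missing is its assignment to the primary outcome.
- **That GEE and an HR are in themselves contradictory.** They are not, because frailty models are offered as the alternative. Only the outcome phrase conflicts.
- **That the trial is underpowered.** The low power figures belong to the less likely reading and rest on assumed heterogeneity and an assumed way for the intervention to act.
- **That a recurrent-event HR would equal the count result exactly.** It would be close, but with unequal practice sizes it need not coincide.

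It can also be said that Protocol 3.9 names no effect measure, so the SAP was free to choose one. That is fair, but Protocol 3.8 does name one and the SAP is silent on replacing it.

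**Conclusion.** The primary analysis sentence is wrong as written, rather than merely short of detail. Its outcome form does not fit its effect measure and coincides with the SAP's own count sensitivity analysis.

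On the likely first-event reading the 1,075 patients remain adequate: about 81% power against 80% for the proportions, given proportional hazards, complete follow-up and the same design effect. The departure from Protocol 3.8 therefore concerns the reported effect measure and its missing justification. It hardly alters the test.

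On the literal count reading, power could lie anywhere from well below 80% to about 90%, and the significance conclusion could differ from that of a first-event analysis. Those ranges are illustrations, because the documents give no event rate per patient and no overdispersion. The judgement on first versus recurrent events is subject to what Appendix 1 contains.

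**What to change.** In the SAP's Primary Outcome Analysis, the primary row of Table 1, and Table 3:

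- Delete the phrase that treats the outcome as a number of events.
- State one primary analysis: time to first AF-related ED visit or unplanned CV admission within 12 months, by a practice-level frailty model adjusted for urban or rural location, reported as an HR with 95% CI. Add the time origin, the censoring rule and the handling of death, which the available text does not give.
- Keep the Poisson count and its IRR as the sensitivity analysis.
- Give the reason for moving from the difference in proportions of Protocol 3.8, and report the clustering-adjusted 12-month risk difference with 95% CI beside the HR.

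Equally acceptable is to make the binary GEE risk difference primary, which matches Protocol 3.8, with the HR and IRR as sensitivity analyses.

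If recurrent events are meant, say so and name a further sensitivity analysis, since the count would then nearly repeat the primary. As a minor correction, the count analysis should not be sent to the baseline table; Table 3 already has an IRR column.

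The cost is SAP wording and table shells. No new data are needed.

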3.7.3 Data Collection

Once informed consent has been obtained by the patient's PCP, a process to record retrospective baseline and ongoing clinical data prospectively will be implemented. Patients will be also requested to complete a patient case report form and quality of life questionnaire (either paper-based or electronic format) to gather relevant demographic and socioeconomic data.

Acknowledging the age profile of AF patients in NS, it is anticipated that a proportion of

CONFIDENTIAL

participants will chose not to complete online surveys or interact with the web-based tool. Completion of the web-based survey tools and / or interacting with the web-based tool, the AF Care Partner, is not mandatory for participation; all survey tools will be available to participants in a paper-based format.

In both study arms, baseline clinical data will be captured from the patient's chart by a data abstractor via on-site visit(s). Abstractors will utilize a laptop computer or tablet to record and transmit study data to secure and password protected servers located behind a firewall at Health Information Technology Services Nova Scotia (HITS-NS). This process will be repeated at 12 months for follow-up data collection in both study arms. Follow-up data for the intervention arm will also be captured through examination of data gathered during use of the CDSS.

The majority of patients at the start of the study are expected to have a past diagnosis of AF. As the study progresses, newly diagnosed patients are anticipated to be enrolled.

Review of PCP records will be done at 12 months to ensure completeness of outcome events. Clinical event / outcomes data will also be captured via review of hospitalization records for consented patients. Patients visiting the AF clinic in Halifax will be consented and data captured during their clinic visit. See Section 4.2 for further details.

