The analysis and reporting of the trial results will follow the CONSORT Statement for cluster-randomization trials [129]. The baseline characteristics of the practices and patients will be reported by group as mean (standard deviation) or median (first quartile, third quartile) for continuous variables, depending on the distribution, and count (percent) for categorical variables. The analysis will follow the intention-to-treat (ITT) principle. The unit of randomization will be the practice. The unit of analysis will be the patient. We will use multiple imputation to handle missing data to enable ITT analysis. Multiple imputation is a Monte Carlo technique in which the missing values are replaced by $m > 1$ simulated versions, where 'm' is typically small. Each of the simulated complete datasets will be analyzed by standard methods, and the results will be combined to produce estimates and confidence intervals that incorporate missing data uncertainty [133]. We will use generalized estimating equations (GEE) – assuming exchangeable correlation structure for patients within the same practice, and adjusting for urban and rural practice types to analyse all outcomes [130]. Unlike ordinary regression techniques, GEE allows us to model the intra-practice correlation among patients within each practice. The results will be reported as the estimate of the effect, corresponding 95% confidence interval and associated p-values. All p-values will be reported to three decimal places with those less than 0.001 reported as $p < 0.001$. The criterion for statistical significance will be set a priori at $\alpha = 0.05$, and adjusted using the Bonferroni method for multiple secondary analyses. All analyses will be performed using SAS 9.4 (Cary, NC).

Sensitivity analyses: 1) There are several methods for analyzing cluster RCTs [131]. Therefore, we will perform sensitivity analyses using some of the commonly used patient-level methods such as random-intercept model and cluster-level (i.e. random- and fixed-effects meta-analytic) methods to assess the robustness of the results. 2) Given that the unit of randomization is the practice, there is a higher chance of potential imbalance of patient-level baseline characteristics. We will perform some sensitivity analysis to adjust for any potential imbalance.

HRQoL

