BLEEDING AND STROKE RISK SCORES		'	
CHA ₂ DS ₂	NOT the value REPORTED in PCP chart.		
Score - Mean (SD) Score - n (%)	CALCULATED using documented RFs.		
0			
1			
2			
3 4			
5			
6			
7			
CHA ₂ DS ₂ -VASc	NOT the value REPORTED in PCP chart.		
Score - Mean (SD) Score - n (%)	CALCULATED using documented RFs.		
0			
1			
2			
3			
5			
6			
7			
8			
9 Bleeding risk: HAS-BLED			
Score - Mean (SD)			
Score - n (%)			
1			
2			
3 4			
5			
6			

7		
7 8		
9		
COEXISTING CONDITIONS - n		
(%)		
Previous stroke, systemic	Stroke (Yes) or SE (Yes) or TIA (Yes)	_
embolism or transient	Stroke (163) of 3E (163) of 11A (163)	
ischemic attack		
Congestive heart failure	HF/LV Dysfunction (Yes)	_
Hypertension	Hypertension (Yes) or (Yes-Treated) or (Yes-	
rrypertension	Not Treated)	
Diabetes mellitus	Diabetes (Yes-Not Documented) or (Yes-Type	
Diabetes memeas	1) or (Yes-Type 2)	
Previous myocardial	MI (MM-YYYY) or (ND)	
infarction	(
Vascular disease (any)	Vascular Disease (Yes)	
CAD	CAD (Yes)	
PAD/PVD	Aortic Plaque (Yes)	
UA	PAD/PVD (Yes)	
MI	UA (date) (MM-YYYY) or (ND)	
Aortic plaque	MI (date) (MM-YYYY) or (ND)	
Valvular Heart Disease	Replacement Type (Mechanical) or Mitral	
	Stenosis Type (Moderate) or (Severe)	
Congenial Heart Disease	Congenital Heart Disease (Yes)	
OSA	OSA Dx (Yes)	
Tobacco use		
Former	Tobacco use (Former)	
Current	Tobacco use (Current)	
Alcohol abuse	Alcohol abuse (Yes)	
Pericarditis	Pericarditis (Yes)	
Pulmonary Disease	Pulmonary Disease (Yes)	
INITEDVENITIONS (DDGGEDUDES		
INTERVENTIONS/PROCEDURES		
- n (%)	Vascular Procedure (Vas)	
Vascular procedure (any) CABG	Vascular Procedure (Yes) CABG (Yes)	
PCI	PCI (Yes)	
Ablation (for flutter or AF)	AF Ablation (Yes) or Previous Ablation for Aflu	_
Ablation from matter of All	(Yes)	
Pacemaker / ICD	Pacemaker (Yes)	
Cardioversion		
# of patients	Cardioversion (Yes)	
# of events – median (IQR)	Cardioversions no.	
Bleeding History - n (%)		

Any bleeding	Bleeding History (Yes)	
Intracranial	IC-Intracerebral (Yes) or IC-Other (Yes)	
Non-intracranial	NIC-Epistaxis (Yes) or NIC-GI (Yes) or NIC-	
Non intractation	Other (Yes)	
Major bleeding	Major bleeding (Yes)	
PAST REFERRALS - n (%)	major precumb (res)	
, ,		
AF Clinic	Referred to (AF Clinic)	
Cardiologist	Referred to (Cardiologist)	
Internist	Referred to (Internist)	
Electrophysiologist	Referred to (Electrophysiologist)	
Cath ablation	Referred to (Cath Ablation)	
ED visit for AF within the last		
12 months	ER Visits (Yes)	
# of patients - n (%)	ED Visits	

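### Anticoagulant therapy is to be compared with urban/rural as the only covariate although baseline anticoagulant status is already collected: a valid analysis, but less precise than it need be

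*SAP*

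**What the plan says.** Both documents give one main model for every outcome: GEE, exchangeable within practice, with practice location as the only covariate. The SAP (Primary Outcome Analysis) has "adjusting for urban and rural practice types to analyze all outcomes"; protocol section 3.9 has "adjusting for urban and rural practice types to analyse all outcomes".

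Anticoagulant therapy is number 6 in the SAP's list of secondary outcomes. SAP Table 2 tabulates the matching baseline drugs ("Vitamin K antagonist (Warfarin" and "Non-vitamin K antagonist (NOAC"), together with anticoagulant contraindication, other reasons for not prescribing, and the stroke and bleeding risk scores. Protocol section 3.7.3 has charts abstracted at baseline and again at 12 months in both arms, and states: "The majority of patients at the start of the study are expected to have a past diagnosis of AF".

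On baseline differences, protocol section 3.9 says "We will perform some sensitivity analysis to adjust for any potential imbalance", naming neither covariates nor outcomes. The SAP says "We will conduct sensitivity analyses in two ways": other methods for clustering, and a Poisson count. Neither uses a baseline covariate. Baseline antithrombotic use appears otherwise only as a subgroup row in SAP Tables 5a-5c, which cover the composite, ED visits and CV hospitalisations.

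**The concern.** Most patients enter with established AF, so whether a patient is anticoagulated at 12 months will often be the baseline status carried forward. A model that ignores that status treats the carried-forward part as noise. Chance differences between practices in earlier prescribing then widen the confidence interval for the change that the trial wants to detect.

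Prescribing for stroke prevention is among the outcomes closest to what a decision support tool can alter, and the protocol's background argues at length that anticoagulation is underused. A wide interval here could make a working tool look inert. The data needed to narrow it are already being collected.

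**Working it through.** **1. The plan's own figure.** The documents give a power calculation only for the primary composite (protocol section 3.8). With z values 1.96 and 0.84, rates 50% and 40%, ICC 0.05 and 9 patients per cluster:

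2 × (1.96 + 0.84)² × (0.50×0.50 + 0.40×0.60) / 0.10² = 2 × 7.84 × 0.49 / 0.01 = 768.32

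768.32 × (1 + 8×0.05) = 768.32 × 1.4 = 1075.6, the stated 1075.

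There is no power or precision figure for anticoagulant therapy, and no rate of use, stopping or starting in the trial population. All such rates below are assumptions.

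**2. Information lost, ignoring clustering.** Let p be the share treated at baseline, a the share of those still treated at 12 months, and b the share of untreated patients who start. The 12-month rate is q = pa + (1−p)b. The baseline-to-12-month correlation is φ = (a−b)·√[p(1−p) / (q(1−q))]. Adjustment multiplies the variance of the risk difference by about 1−φ², so φ² is the share of information lost without it.

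Example: p = 0.80, a = 0.95, b = 0.20 gives q = 0.80, φ = 0.75 and φ² = 0.56.

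| Treated at baseline | Still treated | Untreated who start | φ | Lost |
|---|---|---|---|---|
| 70% | 98% | 10% | 0.89 | 80% |
| 80% | 95% | 20% | 0.75 | 56% |
| 80% | 95% | 30% | 0.68 | 46% |
| 80% | 90% | 30% | 0.58 | 34% |
| 90% | 85% | 40% | 0.34 | 12% |

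Over a grid of 60-90% treated, 85-98% persisting and 10-40% starting, the loss runs from 12% to 80%. It passes one half only when φ exceeds 0.707.

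**3. With clustering.** The variance ratio is [(1−ICC)(1−r_w²)/m + ICC(1−r_b²)] / [(1−ICC)/m + ICC], where r_w and r_b are the within- and between-practice correlations. Take m = 9, r_w = 0.8 and r_b = 0, so that baseline explains none of the practice variation:

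- ICC 0.05: (0.0380 + 0.0500) / (0.1056 + 0.0500) = 0.57, so 43% is lost.
- ICC 0.10: (0.0360 + 0.1000) / (0.1000 + 0.1000) = 0.68, so 32% is lost.

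**4. Power.** Simulation of 120 practices of 9, 75% treated at baseline, ICC 0.05 in baseline use, linear risk-difference model with practice-clustered standard errors, two-sided 0.05, 6,000 replicates. Starts rise by 15 points among the untreated, so the true difference is 0.25 × 15 = 3.75 points.

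| Stop | Start (control vs CDSS) | SE, points | Power | Lost |
|---|---|---|---|---|
| 2% | 10% vs 25% | 2.9 to 1.4 | 26% to 78% | 77% |
| 5% | 20% vs 35% | 2.8 to 1.8 | 28% to 56% | 59% |
| 10% | 30% vs 45% | 2.7 to 2.1 | 27% to 41% | 36% |

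A 1,000-replicate run of the last row gave 34% and 44%. Those do not fit the standard errors: Φ(3.75/2.68 − 1.96) = 0.29 and Φ(3.75/2.14 − 1.96) = 0.42. The larger run is used here.

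If starting and stopping also cluster by practice (ICC 0.10), the loss falls to 51% in the second row (power 24% to 43%) and 29% in the third (23% to 31%). With no true effect (10% stop, 30% start in both arms), both analyses reject 4.8% of the time. Entering baseline as a main effect or also interacted with arm gives the same loss to within 0.2 percentage points.

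**5. Echo, referral and ablation.** Here Table 2 records history (for example "PAST REFERRALS - n"), while the outcome is counted over the 12 months. Plausible combinations give φ from −0.09 to 0.45, so at most 0.45² = 0.20 is lost, and often close to nothing.

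**The case against.** The unadjusted comparison is valid under randomisation, and its standard error already allows for chance imbalance. This is a matter of precision on a secondary outcome, and a trialist may prefer one simple model throughout. That stands, and it limits the point to an improvement rather than an error.

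A reader might infer that the plan throws away more than half the information. The documents do not support that. It needs a correlation above 0.707, no rate in the documents fixes that correlation, and modest changes in assumed stopping or starting bring the loss below half. A reader might also extend the point to echo, specialist consultation and ablation. There the baseline item is a past event rather than an earlier value of the same measure, and the loss is small.

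Two further objections shape the remedy. First, the protocol's outcome (section 2.2) is appropriateness of anticoagulation, whereas the SAP lists therapy and refers to an Appendix 1 that is not in the text supplied. The covariate must match whichever is defined. Second, practices are randomised at recruitment (section 3.7.1) and patients consent later through their provider (section 3.7.3). Status at consent could already reflect allocation, and adjusting for it could absorb part of the effect.

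The protocol's imbalance analysis does not close the gap. It names no covariates, and the SAP does not carry it over.

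**Conclusion.** The point holds for anticoagulant therapy as an avoidable loss of precision, not as bias. Under assumed rates the loss is about 12-80% of the information, and it is smaller where practices differ in starting and stopping as well as in baseline use. Power rose in every scenario simulated, but even the adjusted analysis may fall well short of 80%. These powers are at 0.05; the Bonferroni adjustment in protocol section 3.9 would lower both. The result rests on baseline status being measured before allocation can influence it, and on its being the same measure as the outcome.

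**What to change.** In the SAP's Secondary Outcomes Analysis, before unblinding, state that:

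- The anticoagulant outcome is analysed by GEE clustered on practice, adjusted for urban/rural and for the patient's baseline value of the same measure. That value is anticoagulant use or, if appropriateness is the defined endpoint, baseline appropriateness derived from the Table 2 fields.
- The baseline value is taken from the chart as of the practice's randomisation date or, at the latest, before CDSS access.
- The effect is a standardised risk difference with a practice-clustered 95% CI. A measure has to be named because an adjusted odds ratio is conditional and differs in meaning from the unadjusted one.
- The unadjusted result is kept as a sensitivity analysis.
- Starts among patients untreated at baseline and continuation among those treated are described by arm.

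Either restore the protocol's imbalance analysis with named covariates or state that it has been dropped. Prior echo, past referral and previous ablation may be optional covariates for their own outcomes.

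The cost is a few lines of text, with no new data items. Patients first diagnosed after randomisation need an untreated/not-yet-diagnosed category, and a few others may need a missing-baseline category.
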